### **Size of lesions**

The size (largest diameter) of the 3 most representative lesions will be assessed by off-site readers and on-site radiologists and will be summarized by contrast agent groups and MRI modalities (pre and paired) ; off-site and on-site reader's outcomes will be separately analyzed.

### **Location**

The localization of the 3 most representative lesions will be assessed by off-site readers and on-site radiologists and will be displayed within each organ by contrast agent groups and MRI modalities (pre and paired); off-site and on-site reader's outcomes will be separately analyzed.

Number and percentage of patients by organ will be displayed by contrast agent groups and MRI modalities (pre and paired); off-site and on-site reader's outcomes will be separately analyzed. One patient can have lesions in different organs and so the sum of patients by organ can be greater than the number of patients

The classification of organ will be the following:

Lesion Location	Corresponding organ
Head	Head
Right neck	Neck
Left neck	
Right breast	Breast
Left breast	
Lung	Lung
Liver Right lobe	Liver
Liver Left lobe	
Liver Quadrate lobe	
Liver Caudate lobe	
Gallbladder	Gallbladder
Pancreas	Pancreas
Bile ducts	Bile ducts
Spleen	Spleen
Right adrenal gland	Adrenal gland
Left adrenal gland	
Right kidney	Kidney
Left kidney	
Right urinary tract	Urinary tract
Left urinary tract	
Bowel	Bowel
Retroperitoneum and peritoneum	Retroperitoneum and peritoneum
Bladder	Bladder
Prostate	Prostate
Penis	Penis
Uterus	Uterus
Right ovary and Adnexae (appendages)	Ovary
Left Ovary and Adnexae (appendages)	
Urethra	Urethra
Right upper limb	Limb
Left upper limb	
Right lower limb	
Left lower limb	
Right hand	Hand
Left hand	
Right foot	Foot
Left foot	

#### Diagnostic confidence

The diagnosis for the patient and level of diagnostic confidence according to off-site readers and on-site radiologists will be displayed by contrast agent groups and MRI modalities (pre and paired); off-site and on-site reader's outcomes will be separately analyzed.

Level of diagnostic confidence will be summarized qualitatively and quantitatively by contrast agent groups and MRI modalities (pre and paired); off-site and on-site reader's outcomes will be separately analyzed.

**Impact of contrast-enhanced MRI on patient treatment plan**

The impact on patient treatment plan will be tabulated by contrast agent groups. The therapeutic management proposed based on combined unenhanced and contrast-enhanced MRI vs the one based on unenhanced MRI will be tabulated for all patients having the treatment plan be changed.

The impact on patient treatment plan will be tabulated by contrast agent groups and tumor classification before GBCA administration.

The tumor classification is based on diagnosis done at unenhanced MRI according to the following:

Diagnosis	Tumor classification
Negative	Non Malignant
Benign	Non Malignant
Probably Benign finding	Non Malignant
Low Suspicion of Malignancy	Malignant
Intermediate Suspicion of Malignancy	Malignant
Moderately High Suspicion of Malignancy	Malignant
Not assessable	Not assessable

The impact on patient treatment plan will be fitted by a multiple logistic regression model for correlated data. The model will include the factors contrast agent group and tumor classification before administration (malignant / non malignant / not assessable). The parameters of the model will be estimated using the SAS® procedure glimmix. The difference between contrast agent groups in proportions and associated 95% CI will be computed globally and for each tumor classification.

```
proc glimmix data = XXX;
  class subject GBCA tumor_cl;
  model eval = GBCA tumor_cl GBCA*tumor_cl / dist = bin link =I d ddfm = kr;
  random _residual_ / subject = patient type = cs;
  estimate "gadopiclenol - gadobutrol" GBCA -1 1 /cl;
  estimate "gadopiclenol - gadobutrol for malignant tumor" GBCA -1 1 GBCA*tumor_cl -1 0 0 1 0 0 /cl;
  estimate "gadopiclenol - gadobutrol for non malignant tumor" GBCA -1 1 GBCA*tumor_cl 0 -1 0 0 1 0 /cl;
  estimate "gadopiclenol - gadobutrol for not assessable tumor" GBCA -1 1 GBCA*tumor_cl 0 0 -1 0 0 1 /cl;
run;
```

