#### Non-inferiority of gadopiclenol versus gadobutrol regarding lesion visualization co-primary criteria (primary criteria 2)

CONFIDENTIAL	STATISTICAL ANALYSIS PLAN PHASE III TRIAL GDX-44-011 VERSION NO. 2.0      DATED 25 JANUARY 2021	████████ Page 28 / 57
--------------	---	--------------------------

Each co-primary criterion will be analyzed using a general linear model for each reader independently, modelling the patient's score as a function of the contrast agent group (GBCA: gadopiclenol and gadobutrol) with repeated measures on the patient due to the pairing of contrast agents in patients.

Hence for each off-site reader, the models will be the following:

- Border delineation = contrast agent group + period + error
- Internal morphology = contrast agent group + period + error
- Degree of contrast enhancement = contrast agent group + period + error

The parameters of the general linear model will be estimated using the SAS® procedure Mixed. The procedure used for the non-inferiority analysis will be the following for each co-primary criterion and each off-site reader:

```
proc mixed data = XXX method = REML;
  class subject GBCA period;
  model eval = GBCA period;
  repeated GBCA / subject=subject / type = cs;
/* To get the estimate and the corresponding confidence interval of the paired difference */
  lsmeans GBCA;
  estimate "gadopiclenol - gadobutrol" GBCA 1 -1 /cl;
run;
```

The Student's t-based 95% confidence intervals of the difference between gadopiclenol and gadobutrol will be constructed for each of 3 co-primary criteria using the PPS2 on matching lesions. Results will be presented per off-site reader.

If the lower bound of this confidence interval is above the non-inferiority margin for at least 2 out of 3 readers and for the 3 co-primary criteria, then non-inferiority between gadopiclenol and gadobutrol will be concluded.

As soon as the non-inferiority is demonstrated, the superiority of the gadopiclenol over gadobutrol will be tested using the same method. No adjustment for multiplicity is needed as it is a simple closed testing procedure.

If the lower bound of the Student's t-based 95% confidence intervals of the difference between gadopiclenol and gadobutrol is above 0 for at least 2 out of 3 readers and for the 3 co-primary criteria, then superiority of gadopiclenol over gadobutrol will be concluded.

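### The global treatment-plan contrast weights three tumour classes equally whatever their size, without saying so, and the model omits period

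*SAP*

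**What the plan says.** The analysis is in SAP 5.6.2, under the impact of contrast-enhanced MRI on the patient treatment plan. The text describes a regression for correlated data: "The model will include the factors contrast agent group and tumor classification before administration". The classes are malignant, non-malignant and not assessable, taken from the diagnosis on unenhanced MRI. The text names neither an interaction nor period. It then promises the result: "The difference between contrast agent groups in proportions and associated 95% CI will be computed globally and for each tumor classification".

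The code differs. Its MODEL line is "model eval = GBCA tumor_cl GBCA*tumor_cl / dist = bin link =I d ddfm = kr" and its CLASS line is "class subject GBCA tumor_cl", so the interaction is in and period is in neither statement. The global line is "estimate 'gadopiclenol - gadobutrol' GBCA -1 1 /cl". The by-class lines do write out interaction coefficients; the one for the not-assessable class ends "GBCA -1 1 GBCA*tumor_cl 0 0 -1 0 0 1 /cl". No class weights are stated.

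Elsewhere the SAP does put period in its comparisons of the two agents. Primary analysis 2 (SAP 5.6.1) has, for example, "Border delineation = contrast agent group + period + error", and the E% and LBR models in SAP 5.6.2 also carry it.

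The list of tables (SAP 6.1.2.2) runs this model on Extended FAS 2 as Table 14.2.2.52, after two tabulations: by agent (14.2.2.50) and by agent and class (14.2.2.51).

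**The concern.** A difference reported globally will be read as the difference in the study population. The contrast as coded is that only if the classes are equal in size or share the same difference. Otherwise a class with few patients counts as much as one with many, and its imprecision passes into the overall interval. The text does not warn of this. Nor does it match the code: a model with only agent and class as factors could not produce separate differences by class.

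Period is a separate matter. The on-site reader judges the treatment plan at the end of V2 and again at the end of V4 (Protocol 7.2.8), and Protocol 8.3 asks that, as far as possible, the same radiologist read both examinations. An effect of having seen the V2 images is therefore plausible, and the model has no term for it.

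**Working it through.** The documents give no sample size, rate or power for this endpoint, so there is no figure of the plan's own to reproduce.

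**1. What the global line estimates.** The design has two agents by three classes. With all interaction coefficients at zero, agent -1, +1 is not estimable in this model. With the software's default fill (-1/3 for each class under one agent, +1/3 under the other) it is estimable and equals (d1 + d2 + d3)/3, where d_k is the agent difference in class k. The three by-class lines are estimable as written. If a class has no patients for one agent, the global line is not estimable.

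**2. Width of the interval.** Inputs: n = 200, the evaluable target in SAP 4, used as an illustration. Assumptions not in the documents: response proportion p = 0.30, within-patient correlation 0.5, the two larger classes equal in size, and each patient in the same class at both visits.

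- Variance in class k: v_k = 2p(1-p)(1-0.5)/n_k = 0.21/n_k.
- Equal weights: (v1 + v2 + v3)/9.
- Size weights: 0.21/200 = 0.00105, SE 3.24 points, half-width 1.96 x 3.24 = 6.4 points.
- Ratio of widths, with s_k the class share: the square root of (1/9)(1/s1 + 1/s2 + 1/s3). It does not depend on p, the correlation or n when these are common to all classes.

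Example at 5% (95, 95 and 10 patients): 0.21 x (1/95 + 1/95 + 1/10)/9 = 0.00282, SE 5.31 points, half-width 10.4 points, ratio 1.64.

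| Not-assessable share | Its share of the variance | Width ratio | Half-width, equal vs size weights (points) |
|---|---|---|---|
| 2% | 92% | 2.45 | 15.6 vs 6.4 |
| 5% | 83% | 1.64 | 10.4 vs 6.4 |
| 10% | 69% | 1.27 | 8.0 vs 6.4 |
| 20% | 50% | 1.05 | 6.7 vs 6.4 |
| 33% | 33% | 1.00 | 6.4 vs 6.4 |

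Unequal larger classes change little. For 60/35/5%, (1/9)(1/120 + 1/70 + 1/10) = 0.01362 against 1/200 = 0.005; the square root of 2.72 is 1.65. Shares of 50/40/10% and 55/43/2% give 1.27 and 2.45.

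**3. Point estimate.** If the not-assessable difference departs from a common difference in the other two classes by D, equal weighting moves the global estimate by D x (1/3 - s) relative to size weighting. For D = 20 points that is 6.3 points at 2%, 5.7 at 5%, 4.7 at 10%, 2.7 at 20% and 0 at one third. For D = 0 it is zero at any share.

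**4. Period.** Let f be the share of patients receiving gadopiclenol first and P the period effect. Without a period term the estimate is off by P x (1 - 2f): zero at f = 0.50, and 0.5 to 1.0 point in size at f = 0.55 for an assumed P of 5 to 10 points. The variance of the within-patient difference rises by P squared/0.21: 0.0025/0.21 = 1.2% for 5 points and 0.01/0.21 = 4.8% for 10 points.

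**The case against.** An equal-weight average over classes is a recognised quantity, and its interval is correct for that quantity. This stands. The complaint is not that the interval is invalid, but that the SAP neither states the weighting nor leads the reader to expect it.

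A reader might infer that a small not-assessable class will drive the overall result. The documents do not support that. They give no class sizes, and because the class comes from unenhanced images in patients referred for a contrast examination, it need not be rare. Extended FAS 2 requires assessable paired images for both agents, which may point to a small class, but that is inference. At a 20% share the effect on width is 5%, and at one third it vanishes.

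A reader might also infer that omitting period worsens the weighting or biases the comparison. It does not change the class weights, and with 1:1 allocation in blocks there is no bias at balance. No passage gives the size or direction of a period effect. Nor is the SAP's practice uniform: the code comparing lesion counts between agents also lacks period, although its text names it. What remains is that Extended FAS 2 keeps only patients with both examinations assessable, and SAP 4 itself foresees unequal drop-out between series.

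Finally, the two tabulations will show the crude proportions by agent and the class counts, so an odd global line would be visible. This limits the harm.

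**Conclusion.** The point holds in a conditional form and is minor. From the code alone it is certain that the global difference is an unweighted mean over three classes, that it fails if a class is empty for one agent, and that period is absent. How much the weighting matters depends on class sizes that the documents do not give. The interval is about 2.45 times as wide as under size weighting at a 2% share, 1.65 at 5% and 1.27 at 10%, and the difference is negligible from about 20% upward. These ratios assume the same response rate and correlation in every class, and one class per patient. The estimate shifts only if the not-assessable class behaves differently.

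Leaving out period is a separate and smaller defect: about 1 point at a 55:45 split with an assumed 10-point effect, and a variance increase of 1% to 5%. The endpoint is secondary, read on site and carries no success rule. No primary conclusion depends on it, and the crude table by agent is unaffected.

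**What to change.** 1. In the global ESTIMATE, write the interaction coefficients explicitly as the observed class frequencies w1, w2, w3 (summing to 1): `GBCA -1 1 GBCA*tumor_cl -w1 -w2 -w3 w1 w2 w3`. Define the frequencies as pooled over both visits, because class is assessed at each unenhanced MRI and a patient may change class between agents.
2. Keep the interaction model for the by-class differences. Dropping the interaction for the global line is a less exact alternative: it gives an information-weighted common difference, which need not equal the population difference.
3. Add period to the CLASS and MODEL statements.
4. Have the text name the interaction, period and the weights, so that text and code agree.
5. State what is reported if a class is empty for one agent, since frequency weights do not cure that.

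The cost is a few words of SAP text and code. No new data are needed.

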**Percentage Enhancement of lesions (E%)**

E% is calculated from the Signal Intensity (SI) measurement of maximum 3 most representative lesions by the 3 independent off-site readers. The mean of E% will be calculated by patient using only matching lesions between GBCA

For each reader, E% will be tabulated by contrast agent groups using FAS 2. Differences between contrast agents will be tested using a Student's t-test. The models will include the contrast agent group and the period. The parameters of the general linear models with repeated measures will be estimated using the SAS® procedure Mixed. The difference between contrast agent groups in mean score and associated 95% two-sided CI will be computed.

The SAS® procedure used for the analysis will be the following:

```
proc mixed data = XXX method = REML;
  class subject GBCA period;
  model eval = GBCA period;
  repeated GBCA/subject= subject / type = cs;
  lsmeans GBCA / pdiff = control('gadobutrol') tdiff cl alpha = 0.025;
  /* The following code is needed as previous statement lsmeans does not provide the upper limit of CI */
```

CONFIDENTIAL	STATISTICAL ANALYSIS PLAN PHASE III TRIAL GDX-44-011 VERSION NO. 2.0      DATED 25 JANUARY 2021	████████ Page 39 / 57
--------------	---	--------------------------

lsmeans GBCA;  
estimate "gadopiclenol - gadobutrol" GBCA 1 -1 /cl;  
run; .

### **Lesion to Background Ratio (LBR)**

LBR is calculated from the SI measurement of maximum 3 most representative lesions by the 3 independent off-site readers. Then, the mean of LBR will be calculated by patient and by MRI modality using only gadopiclenol-gadobutrol matching lesions. Only pre-contrast lesions which match with those gadopiclenol-gadobutrol matching lesions will be kept in the analysis and descriptive statistics.

For each reader, LBR will be tabulated by contrast agent groups on pre contrast and paired images using FAS 2.

Differences between contrast agents will be tested using a Student's t-test. The models will include the contrast agent group, the period and the unenhanced value (pre) as covariate. The parameters of the mixed models will be estimated using the SAS® procedure Mixed. The difference between contrast agent groups in mean score and associated 95% two-sided CI will be computed.

Procedure used will be the following for each off-site reader:

```
Proc mixed data = XXX method = REML;
  class subject GBCA period;
  model eval = GBCA period pre;
  repeated GBCA/subject= subject / type = cs;
  lsmeans GBCA / pdiff = control('gadobutrol') tdiff cl alpha = 0.025;
/* The following code is needed as previous statement lsmeans does not provide the upper limit of CI */
  lsmeans GBCA;
  estimate "gadopiclenol - gadobutrol" GBCA 1 -1 /cl;
run; .
```

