1.2 Background

The use of GBCAs for MRI has revolutionized the radiologic field since their introduction 30 years ago. These contrast agents have been used extensively in a large range of indications such as CNS and body, the latter including head & neck, thorax (including breast), abdomen (including liver, pancreas, and kidney), pelvis (including uterus, ovary and prostate), and musculoskeletal (including extremities). While helical computed tomography (CT) has been the workhorse of most radiology departments, recent advances in MRI have moved it to the forefront of oncologic imaging for various body regions. Compared to CT, MRI of body regions, such as abdomen and pelvis, offers important advantages, including superior soft-tissue contrast. The multiplanar capabilities of MRI allow for direct coronal or sagittal imaging, providing a more accurate anatomic presentation of abdominal and pelvic masses. Among the recent advances in MRI are faster pulse sequences, breath-hold imaging, and use of intravenous contrast agents and surface coils, all of which have improved image quality and shortened examination times. The versatility of MRI is unmatched by any other imaging examination. For these reasons, MRI has evolved from a problem-solving study to become the primary imaging examination in many patients with malignancy. The imaging evaluation of oncology patients requires accurate depiction and characterization of tumors.

Liver MRI: the depiction of a focal liver lesion requires a difference in signal intensity between the lesion and the adjacent liver parenchyma. The lesion may be either more or less intense than the

 CONFIDENTIAL	Protocol No. GDX-44-011 Version No. 3.0 (including amendment 2) June 30, 2020	Page 24 / 82
--	---	--------------

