surrounding liver tissue. Most liver masses are easily depicted on unenhanced T1-weighted or T2-weighted MRIs. However, some tumors produce minimal changes in T1- and T2-relaxation and, therefore, show limited contrast with the surrounding liver. Contrast agents are used to accentuate the inherent differences in liver-lesion signal intensity. These contrast agents facilitate differential enhancement of liver parenchyma and masses, as well as promote lesion depiction and, to some degree, lesion characterization [1, 2]. Gadolinium chelates rapidly equilibrate from the intravascular space into the extracellular space after injection. The use of gadolinium chelates has become an integral part of MRI of the liver and extrahepatic abdomen. Gadolinium chelates uniquely provide important information about tumor perfusion, which is key in the assessment of liver masses. They assist with the detection and characterization of liver lesions and in the establishment of the volume of viable perfused tumor. Gadolinium chelates are equally important for MRI of the extrahepatic abdomen. The interstitial accumulation of these agents within peritoneal, omental, and gastrointestinal tumor produces marked enhancement and is crucial to accurate tumor staging. Depiction of lesions within solid visceral organs, such as the pancreas, kidneys, and spleen, also improves following gadolinium injection [3, 4].

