- Chemotherapy
- Radiotherapy
- Other treatment: specify

7.2.9 ***Percentage enhancement (E%) of lesion and Lesion to Background Ratio (LBR) (off-site read)***

The 2 quantitative criteria (E% and LBR) will be calculated by patient in averaging the parameter for maximum 3 most representative lesions.

 CONFIDENTIAL	Protocol No. GDX-44-011 Version No. 3.0 (including amendment 2) June 30, 2020	Page 42 / 82
---	---	--------------

- Percentage enhancement (E%) of lesion

$$E\% = \frac{SI_{post} - SI_{pre}}{SI_{pre}} \times 100$$

where SI_{post} = Signal intensity of lesion on post injection images
 SI_{pre} = Signal intensity of lesion on pre injection images

- Lesion to Background Ratio (LBR) (pre and post)

$$LBR = \frac{SI_{lesion}}{SI_b}$$

where SI_{lesion} = Signal intensity of lesion
 SI_b = Signal intensity of background (surrounding healthy tissue of the lesion)

7.2.10 *Overall diagnostic preference (off-site read)*

The evaluation will be performed in a global matched-pairs fashion (images set 1b or 2b). For each patient who received the two different IMPs, all images (paired image set 1b or 2b) from the first MR examination, labeled as examination 1, will be displayed simultaneously with the corresponding paired images from the second MR examination, labeled as examination 2.

The assessment will be performed based on 3-point scale:

- 1: When examination 1 is preferred to examination 2
- 0: When no preference is observed
- 2: When examination 2 is preferred to examination 1

IBRs need to select one or more of the following six reasons for this preference:

- Contrast enhancement was superior,
- Delineation of normal structure was better
- Delineation of at least one lesion was better
- Internal structure of lesions was better visualized
- More lesions were identified
- Diagnostic confidence was greater (specify one or more reason(s): detection of lesions, characterization of disease, assignment of a grade to disease, definition of extent of disease, or other reasons that had to be specified on the Imaging eCRF)

7.2.11 *Safety profile of gadopiclenol and gadobutrol (on-site)*

The safety assessments will be followed up by evaluating results of vital signs, injection site tolerance, clinical laboratory parameters (blood samples) and adverse events (AEs) reporting.

○ **Vital signs**

Vital signs (supine systolic and diastolic blood pressures, pulse rate) will be measured and recorded according to the following schedules:

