Diagnostic confidence will be tabulated by contrast agent groups; off-site and on-site reader's outcomes will be separately analyzed.

Impact of contrast-enhanced MRI on patient treatment plan:

The impact on patient treatment plan will be assessed by on-site radiologists and will be tabulated by contrast agent groups.

Percentage enhancement (E%) of lesion

E% is calculated from the Signal Intensity (SI) measurement of maximum 3 representative lesions by the 3 independent off-site readers (see [section 7.2.9](#)).

For each reader, E% will be tabulated by contrast agent groups and differences between contrast agents will be tested using a Student's t-test.

 CONFIDENTIAL	Protocol No. GDX-44-011 Version No. 3.0 (including amendment 2) June 30, 2020	Page 68 / 82
--	---	--------------

Lesion to Background Ratio (LBR)

LBR is calculated from the Signal Intensity (SI) measurement of maximum 3 representative lesions by the 3 independent off-site readers (see [section 7.2.9](#)).

For each reader, LBR will be tabulated by contrast agent groups and differences between contrast agents will be tested using a Student's t-test.

Overall diagnostic preference

For each off-site reader, the overall diagnostic preference will be tabulated and gadopiclenol will be compared to gadobutrol by a Wilcoxon signed-rank test.

The reason of this preference will be displayed according to the contrast media preferred.

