CONFIDENTIAL	STATISTICAL ANALYSIS PLAN PHASE III TRIAL GDX-44-011 VERSION NO. 2.0      DATED 25 JANUARY 2021	████████
--------------	---	----------

- Percentage enhancement (E%) of lesion

$$E\% = \frac{SI_{post} - SI_{pre}}{SI_{pre}} \times 100$$

where  $SI_{post}$  = Signal intensity of lesion on post injection images  
 $SI_{pre}$  = Signal intensity of lesion on pre injection images

- Lesion to Background Ratio (LBR)

$$LBR = \frac{SI_{lesion}}{SI_b}$$

where  $SI_{lesion}$  = Signal intensity of lesion  
 $SI_b$  = Signal intensity of background (surrounding healthy tissue of the lesion)

- Overall diagnostic preference (off-site read)

The evaluation will be performed in a global matched-pairs fashion and preference will be determined on a 3-point scale:

- 1: when examination 1 is preferred to examination 2
- 0: when no preference is observed
- 2: when examination 2 is preferred to examination 1

Reason for preference will also be recorded according to the following:

- Contrast enhancement was superior,
- Delineation of normal structure was better
- Delineation of at least one lesion was better
- Internal structure of lesions was better visualized
- More lesions were identified
- Diagnostic confidence was greater (specify one or more reason(s): detection of lesions, characterization of disease, assignment of a grade to disease, definition of extent of disease, or other reasons that had to be specified on the eCRF)

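### The raw mean lesion-to-background ratio compares relative lesion brightness between agents, not lesion contrast, because contrast gains in brighter and darker lesions enter with opposite signs

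*SAP*

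**What the plan says.** SAP 2.2.2 and Protocol 7.2.9 define LBR as lesion signal intensity divided by the signal intensity of the surrounding healthy tissue. Protocol 7.2.9 adds: "The 2 quantitative criteria (E% and LBR) will be calculated by patient in averaging the parameter for maximum 3 most representative lesions". SAP 5.6.2 narrows this to lesions matched between the agents: "the mean of LBR will be calculated by patient and by MRI modality using only gadopiclenol-gadobutrol matching lesions".

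Protocol 11.3.6 says that, for each reader, "LBR will be tabulated by contrast agent groups and differences between contrast agents will be tested". SAP 5.6.2 repeats the plan ("Differences between contrast agents will be tested using a Student's t-test") and implements it on FAS2 as a mixed model with agent, period and the pre-contrast LBR, reporting a two-sided 95% interval. Neither document takes logs, measures distance from 1, separates lesions by polarity, or says which direction of LBR is favourable.

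On liver imaging, Protocol 1.2 says that depiction depends on a signal difference between lesion and parenchyma, and then: "The lesion may be either more or less intense than the" surrounding liver. It continues: "Contrast agents are used to accentuate the inherent differences in liver-lesion signal intensity".

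**The concern.** An LBR of 1 means that the lesion cannot be told from its background by signal. Contrast improves as the ratio moves away from 1 in either direction. If an agent accentuates an existing difference, LBR rises in a lesion brighter than its surroundings and falls in a darker one. Averaging raw ratios adds these opposite movements together, within a patient who has both kinds of lesion and again across patients.

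LBR is one of two quantitative off-site criteria. The other, percentage enhancement, uses lesion signal only, so LBR is the only quantitative measure that sets the lesion against its surroundings. It also receives a formal test and an interval for each reader. What is at stake is whether that comparison can be read as better or worse lesion contrast.

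**Working it through.** The documents give no expected LBR, standard deviation, power or direction, so there is no planned figure to reproduce. The definition and the averaging rule come from SAP 2.2.2 and 5.6.2. Every LBR value, contrast gain and share of dark lesions (q) below is an assumption.

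**Within one patient.** Take one bright and one dark lesion: 1.5 and 0.5 with agent A, 1.6 and 0.4 with agent B. Agent B shows both lesions more distinctly.
- Raw mean: A (1.5 + 0.5)/2 = 1.00; B (1.6 + 0.4)/2 = 1.00. The difference is 0, and both sit at the no-contrast value.
- Mean |ln LBR|: A (0.405 + 0.693)/2 = 0.549; B (0.470 + 0.916)/2 = 0.693.

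**Across lesions.** Let LBR be b in bright lesions and 1/b in dark ones, and let the better agent multiply |ln LBR| by k. The raw mean difference is (1 − q)(b^k − b) + q(b^−k − b^−1). With b = 1.5 and k = 1.2 (a 20% gain):
- bright lesion: 1.627 − 1.500 = +0.127
- dark lesion: 0.615 − 0.667 = −0.052
- break-even: q = 0.127/(0.127 + 0.052) = 0.71

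For b from 1.3 to 2.0 and k of 1.1 or 1.2, the break-even runs from 0.63 to 0.82. If bright and dark lesions sit symmetrically on the raw scale (1 + c and 1 − c), it is 0.50.

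**Simulation.** 1000 runs; 200 patients with 1 to 3 lesions each; |ln LBR| about 0.4; true gain 20%; lesion noise SD 0.25 on the log scale; paired t-test without period or pre-contrast covariate. The second and third columns come from the formula above, the last two from the simulation.

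| Dark share q | Raw difference | Share of full difference kept | Raw LBR significant for the better agent | Mean \|ln LBR\| significant for the better agent |
|---|---|---|---|---|
| 0 | +0.127 | 100% | 98.6% | 97.8% |
| 0.1 | +0.109 | 86% | 96.0% | 97.9% |
| 0.2 | +0.091 | 72% | 91.5% | 98.1% |
| 0.3 | +0.073 | 58% | 82.8% | 98.1% |
| 0.5 | +0.037 | 30% | 39.2% | 98.5% |
| 0.7 | +0.002 | 1% | 3.5% | 97.9% |

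Raw LBR is significant in the wrong direction in 0.9% of runs at q = 0.7, 46% at q = 0.9 and 97.8% at q = 1.

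**A second set of values.** Better agent 2.0 (bright) and 0.5 (dark); weaker agent 1.43 and 0.70. The bright difference is +0.571 and the dark difference −0.200. The mixture gives +0.379 at q = 0.25, +0.186 at 0.5 and −0.007 at 0.75. It breaks even at 0.571/(0.571 + 0.200) = 0.74.

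**The pre-contrast covariate.** It enters as one slope on the raw scale. It adjusts for starting brightness but does not turn a downward movement in a dark lesion into a gain.

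**The case against.** Four arguments stand against the point.

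1. The plan never says that a higher LBR is better. The LBR code uses the two-sided `control('gadobutrol')`, whereas the superiority model uses the one-sided `controlu`. This stands: the plan cannot be charged with a wrong direction rule. But with no direction stated, the report has no rule for reading a difference.

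2. Lesion selection favours enhancement. Patients enter with known or suspected enhancing lesions (Protocol 4.1), and the largest enhancing lesions are to be prioritised on paired reads (Protocol 7.1.1). This stands in part, since it should lower the dark share. It does not guarantee LBR above 1, because background can enhance more than the lesion. The exclusion for having no matching enhancing lesion acts on PPS2, while LBR is analysed on FAS2.

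3. The polarity statement concerns liver only, and no liver count is planned. The minimum of 50 abdomen patients covers a mixed region. This stands, and the size of the effect in this trial is therefore unknown.

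4. Border delineation, a co-primary criterion, captures distinction from surrounding tissue whatever the polarity, and signal intensities will be listed (SAP 6.2.6.2), so polarity can be examined later. Both are true. However, a qualitative score does not make the LBR test interpretable, and orienting LBR after seeing the data would be data-driven.

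A reader might go further and infer that the LBR difference has no interpretable direction, or that the better agent is likely to look worse. The documents support neither. Raw LBR has a clear meaning as relative brightness, and under the assumed values the sign holds until dark lesions reach about half or more.

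**Conclusion.** The point holds in limited form. As planned, the LBR comparison estimates a difference in relative lesion brightness. It equals a difference in lesion contrast only if nearly all lesions are brighter than background, which neither document establishes and Protocol 1.2 contradicts for liver.

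The likely consequence is attenuation: under the assumed values, 72% of the raw difference survives at 20% dark lesions and 30% at 50%. Reversal needs dark lesions to exceed about 50-80%. These figures rest on assumed ratios, an assumed uniform 20% gain and an unknown dark share. The steady performance of |ln LBR| also depends on having built the gain to be equal on the log scale for both polarities.

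LBR is a secondary criterion with no success rule. The primary objectives, the sample size and the decision rules are unaffected. A correction is worthwhile because it is cheap and changes what the LBR comparison can conclude.

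**What to change.** - Keep the raw LBR model in SAP 5.6.2 as the protocol-defined analysis, and state that its difference is read as relative lesion brightness only.
- Before unblinding, prespecify a second analysis: compute |ln(LBR)| for each lesion, average per patient over the same matching lesions, and compare agents by reader in the same repeated-measures model with agent and period. Base any statement about better or worse lesion contrast on this analysis. Do not carry a folded pre-contrast value across as covariate without justification: 0.70 and 1.43 both become 0.357, although brightening of the lesion moves one towards 1 and the other away from it.
- Tabulate raw LBR by lesion polarity (LBR ≥ 1 and < 1).
- Do not substitute max(LBR, 1/LBR), which ranks patients differently once averaged. Lesions at 1.0 and 3.0 give mean |ln| 0.549 and mean max 2.0; lesions at 1.8 and 1.8 give 0.588 and 1.8.

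The cost is SAP wording and one derived variable from signal intensities already collected. The downsides are a less familiar unit, and absolute values that noise inflates when LBR is near 1.
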